17.3.3. SUBGROUP ANALYSIS OF LABORATORY VALUES

The following laboratory parameters will be evaluated for the subgroups specified in section 7.5: serum prolactin, blood glucose, HOMA-IR, HbA1c (NGSP), glycoalbumin (absolute and percentage), total cholesterol, LDL cholesterol, HDL cholesterol and triglycerides. These parameters will be separated by fasting status (as applicable) for the subgroup analyses.

Observed and change from DB baseline and LT baseline summaries for clinical chemistry and hematology parameters will be presented for all subjects up to Week 28 overall and by country (excluding Japan) separately, and repeated for all Japanese subjects up to Week 52 separately as well. For the above selected clinical chemistry parameters the observed and change from DB baseline and TL baseline summaries will be repeated for all subjects up to Week 28 by Sex subgroup, all Japanese subjects up to Week 52 by Sex, Age and Mood Stabilizer subgroups separately as well.

Shifts from DB baseline and LT baseline summaries for clinical chemistry and hematology parameters will be presented for all subjects up to Week 28 and repeated for all Japanese subjects up to Week 52 as well. Shift from DB baseline and LT baseline for Prolactin will be presented overall and by Sex.

Number and percentage of MAPVL summaries will be presented for all subjects up to Week 28 overall and will be repeated for all Japanese subjects up to Week 52 separately as well.

17.4. ECG EVALUATIONS

Results from the central [REDACTED] will be included in the reporting of this study. ECG results will be summarized by treatment group for the safety population.

A Week 28 (LOCF) endpoint and Week 52 (LOCF) endpoint (only for subjects in Japan) will also be derived for ECG. For calculation details, please see section 6.3.

The following ECG parameters will be reported for this study:

- Heart Rate (bpm)
- PR Interval (msec)
- QRS Interval (msec)
- QT Interval (msec)
- QTcB Interval (msec): QTc Interval using Bazett's correction
- QTcF Interval (msec): QTc Interval using Fridericia's correction
- RR Interval (msec)
- Overall assessment of ECG (Investigator's judgment):
 - o Normal
 - o Abnormal

The following summaries will be provided for ECG data:

- Observed, DB baseline and LT baseline and change from DB baseline and LT baseline by visit (for quantitative measurements)
- Shift from DB baseline and LT baseline to Week 28 (LOCF) and Week 52 (LOCF) endpoints according to abnormal criteria (for overall assessment)

Document: K:\DSP\SM-13496\RVA97109\Biostatistics\Documentation\SAP

Author: [REDACTED]

Version Number: 1.0

Version Date: 20MAR2018

Template No: CS_TP_BS016 – Revision 3

Reference: CS_WI_BS005

Effective Date: 01May2012

Copyright © 2012 [REDACTED] All rights reserved.

The contents of this document are confidential and proprietary to [REDACTED].

Unauthorized use, disclosure or reproduction is strictly prohibited.

- Summary of subjects with abnormal ECG values (see section 17.4.2)
- Incidence of QTc Prolongation (see section 17.4.3)
- Listing of subjects with prolonged QTc results

17.4.1. ECG SPECIFIC DERIVATIONS

All required ECG parameters are available in the data provided for analysis. There are no ECG parameters to be derived.

17.4.2. ECG ABNORMAL CRITERIA

The individual ECG measurements would be noted as abnormal if exceeding the values indicated in Table D.

Table D: **Abnormal ECG Values by parameter**

ECG Parameter	Abnormal
HR (bpm)	≥ 100 bpm
PR interval (msec)	≥ 210 msec
QRS interval (msec)	≥ 120 msec
QT interval (msec)	> 500 msec

17.4.3. ECG MARKEDLY ABNORMAL CRITERIA (QTc PROLONGATION)

Markedly abnormal quantitative post-baseline ECG measurements will be identified in accordance with the following predefined markedly abnormal criteria:

- Absolute values for QTcB interval and QTcF will be classified as:
 - Male > 450 msec or Female > 470 msec
 - > 450 msec
 - > 480 msec
 - > 500 msec
- Change from Baseline for QTcB interval and QTcF will be classified as:
 - ≥ 30 msec increase from baseline
 - ≥ 60 msec increase from baseline

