6.2. BASELINE

For subjects who completed the prior double-blind study, the double-blind baseline (DB baseline) is defined as the last non-missing assessment (including unscheduled assessments) collected on or prior to the reference start date of the prior double-blind study (D1002001). In the case where the last non-missing assessment and the reference start date coincide, that assessment will be considered pre-baseline, but AEs and medications commencing on the reference start date will be considered post-baseline. The long-term baseline (LT baseline) is defined as Week 6 of the prior double-blind study (D1002001).

For subjects who did not participate in the prior double-blind study, DB baseline is not defined, and LT baseline is defined as the last non-missing assessment (including unscheduled assessments) collected on or prior to the reference start date of the long-term study (D1002002). In the case where the last non-missing assessment and the reference start date coincide, that assessment will be considered pre-baseline, but AEs and medications commencing on the reference start date will be considered post-baseline.

Post-baseline data will be defined as non-missing data on or after Day 1 and through 7 days after the final administration of study medication in the treatment phase (excluding baseline).

In the event that data recorded in the prior double-blind study (D1002001) would actually be collected after the reference start date of the long-term study (D1002002), this data will be included in this long-term study in looking for maximum on treatment values, but will not be taken into account for any other summaries.

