17.5.2. VITAL SIGNS MARKEDLY ABNORMAL CRITERIA

Markedly abnormal quantitative Vital Signs measurements will be identified in accordance with the following predefined markedly abnormal criteria indicated in Table E.

Document:	K:\DSP\SM-13496\RVA97109\Biostatistics\Documentation\SAP	Version Number:	1.0
Author:	[REDACTED]	Version Date:	20MAR2018

Template No: CS_TP_BS016 – Revision 3
Effective Date: 01May2012

Reference: CS_WI_BS005

Copyright © 2012 [REDACTED] All rights reserved. [REDACTED] Unauthorized use, disclosure or reproduction is strictly prohibited.

Table E: Criteria for Markedly Abnormal Vital Signs

Variable	Unit	Low	High
Pulse rate	Bpm	≤ 50 bpm AND change from baseline ≤ -15 bpm	≥ 120 bpm AND change from baseline ≥ 15 bpm
SBP	mmHg	≤ 90 mmHg AND change from baseline ≤ -20 mmHg	≥ 180 mmHg AND change from baseline ≥ 20 mmHg
DBP	mmHg	≤ 50 mmHg AND change from baseline ≤ -15 mmHg	≥ 105 mmHg AND change from baseline ≥ 15 mmHg
Body temperature	°C	NA	≥ 38.3 °C AND change from baseline ≥ 0.8 °C
Weight	Kg	percentage change from baseline ≤ -7.0 %	percentage change from baseline ≥ 7.0 %

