17.5.3. SUBGROUP ANALYSIS OF VITAL SIGNS VALUES

Observed, DB baseline and LT baseline and change from DB baseline and LT baseline by visit analyses will be repeated for all subjects up to Week 28 and repeated for Japanese subjects up to Week 52 separately as well.

For weight and BMI measurements only, summaries for observed, DB baseline and LT baseline and change from DB baseline and LT baseline at Weeks 28 and 28 (LOCF) will be repeated for all subjects up to Week 28 overall and by country (excluding Japan) as well as at Weeks 52 and 52 (LOCF) for all Japanese subjects up to Week 52 overall, by Sex, Age and Mood Stabilizer subgroups separately as well.

Incidence of markedly abnormal post LT baseline vital signs (MAPVS) will be repeated for all subjects up to Week 28 as well as for all Japanese subjects up to Week 52 separately as well.

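### The QTc-increase and 7% weight-change categories do not say which of two baselines they use; from the LT baseline, LUR-LUR counts would omit change from the first 6 weeks of lurasidone

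*SAP*

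**What the plan says.** SAP 6.2 gives prior-study completers two reference points. For them "the double-blind baseline (DB baseline) is defined as the last non-missing assessment (including unscheduled assessments) collected on or prior to the reference start date" of D1002001, and "The long-term baseline (LT baseline) is defined as Week 6 of the prior double-blind study (D1002001". New recruits have only one: "For subjects who did not participate in the prior double-blind study, DB baseline is not defined", and their LT baseline is the last value on or before the first dose in the long-term study.

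The categorical rules do not carry this distinction through.

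- SAP 17.4.3 introduces the increases of 30 and 60 msec or more with "Change from Baseline for QTcB interval and QTcF will be classified as", with no DB or LT.
- SAP 17.5.2, Table E, uses "percentage change from baseline ≥ 7.0" per cent for high weight (and the mirror image for low), again unqualified. The pulse, blood pressure and temperature rows of Table E are worded in the same way.
- SAP 17.5.3 says "Incidence of markedly abnormal post LT baseline vital signs (MAPVS) will be repeated" for all subjects and for Japanese subjects. This is the only pointer to LT, and it concerns vital signs alone.
- Protocol 9.6.5 asks for the incidence of markedly abnormal vital signs and prolonged QTc, and names no reference for change.

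**The concern.** A programmer could use either baseline for the QTc categories and comply with the SAP. For weight, the wording of 17.5.3 leans towards LT.

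The choice matters because the LT baseline means different things in different groups. LUR-LUR subjects were randomised to lurasidone in D1002001, so their Week 6 value is on-drug. PBO-LUR subjects were on placebo at Week 6, and NR-LUR subjects had not started study drug. Under LT, a LUR-LUR subject is flagged only if the change after Week 6 reaches the threshold by itself, while subjects in the other two groups are flagged on change since starting lurasidone. The same column label would describe two different quantities, and ALL-EXT would add them together.

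At stake is how many subjects had a QTc rise of 30 or 60 msec, or a weight change of 7%, since starting the drug. These counts are a natural safety reading for a long-term study.

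**Working it through.** The documents give no incidence, mean or SD for QTc or weight change, so there is no figure to reproduce. The check sets the definitions side by side and asks whether the choice of baseline can change who is counted.

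**1. What each baseline is, by group (SAP 3.3 and 6.2)**

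| Group | DB baseline | LT baseline | LT relative to lurasidone |
|---|---|---|---|
| LUR-LUR | before first dose in D1002001 | Week 6 of D1002001 | after 6 weeks on drug |
| PBO-LUR | before first dose in D1002001 | Week 6 of D1002001 | before lurasidone, after placebo |
| NR-LUR | not defined | on or before first long-term dose | before lurasidone |

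**2. Can the choice change who is flagged?** Take an invented LUR-LUR subject.

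- QTc 400 (DB), 418 (LT), 434 msec (later): 434 − 418 = +16 from LT, not flagged; 434 − 400 = +34 from DB, flagged at 30.
- Weight 70, 73, 76 kg: 76/73 − 1 = +4.1% from LT, not flagged; 76/70 − 1 = +8.6% from DB, flagged at 7%.

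If the early change is a fall, the result reverses. With weight 73, 70, 76 kg the change is +8.6% from LT (flagged) and +4.1% from DB (not flagged). So the choice matters, but its direction depends on the data.

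**3. Do the other planned outputs recover the count?**

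- Mean change from DB does not give the number of subjects past a threshold.
- The absolute QTc categories start above 450 msec; the subject at 434 msec passes unseen.
- BMI shifts register only a change of category. A BMI going from 22.0 to 23.6 is 23.6/22.0 − 1 = +7.3%, and stays within the SAP's normal band of 18.5 to below 25.

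**4. How large could it be?** All means and SDs here are assumptions. Let the weight change from DB to LT have mean m1 and SD s1, and from LT to endpoint mean m2 and SD s2 (all in %), normal and independent.

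P(7% or more from LT) = 1 − Φ((7 − m2)/s2)

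P(7% or more from DB) = 1 − Φ((7 − m1 − m2)/√(s1² + s2²))

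| m1, s1, m2, s2 | From LT | From DB | DB-flagged but not LT-flagged (simulation) |
|---|---|---|---|
| 0, 2.5, 0.5, 5 | 1 − Φ(1.30) = 9.7% | 1 − Φ(6.5/5.59) = 12.2% | 40% |
| 0.5, 2.5, 1, 5 | 1 − Φ(1.20) = 11.5% | 1 − Φ(5.5/5.59) = 16.3% | 42% |
| 1, 3, 1, 5 | 1 − Φ(1.20) = 11.5% | 1 − Φ(5/5.83) = 19.6% | 51% |

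These results depend heavily on the inputs. In the second row, holding the SD at 5 from either baseline gives 1 − Φ(5.5/5) = 13.6% from DB. So 16.3 − 13.6 = 2.7 of the 4.8-point gap comes from the variance assumption.

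For QTc, assume an SD of 14 msec from either baseline, no later mean shift, and an early shift of 5 msec. The incidence of 30 msec or more is 1 − Φ(30/14) = 1.6% from LT and 1 − Φ(25/14) = 3.7% from DB. With no early shift, both are 1.6%.

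**5. How much of ALL-EXT has an on-drug LT baseline?** The targets are 325 completers and 80 new recruits, 405 in all (Protocol 3.5). The documents do not give the prior study's allocation. If 50% to 75% of completers came from a lurasidone arm, the share is 325 × 0.50/405 = 40% to 325 × 0.75/405 = 60%.

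**The case against.** The strongest reply is that little is hidden. A reader might infer that change in the first 6 weeks of lurasidone is lost from the safety analysis. The documents do not support that. Change from DB is planned for ECG parameters (SAP 17.4, with QTcB and QTcF in 17.4.4) and for weight and BMI (17.5, 17.5.3). BMI category shifts use both baselines. A further set of QTc categories, under "Absolute values for QTcB interval and QTcF will be classified as", needs no baseline. Protocol 3.4.2 lists change in QTc and body weight from both studies' baselines as the safety variables, and those analyses are fully planned. Only the threshold-of-change counts are exposed.

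A reader might also infer that the SAP uses LT for the 30 and 60 msec categories. No ECG section says so. Even for weight, the words in 17.5.3 may only fix the observation window, as similar wording does in Protocol 9.3.5. The output templates mentioned in SAP 8 are not among the documents; they may name the baseline.

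Nor do the documents support saying that the incidences are understated. That needs an upward early shift or added early variability, and neither is documented. The models in the working also use a single endpoint value, whereas the incidence covers all post-baseline values.

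Two further points have force. Results are shown by prior treatment group, so a reader can see which groups had an on-drug Week 6 value. And change from entry into the long-term study is a legitimate question in its own right.

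What remains is that the reference is not named, and an LT-only table could not answer how many LUR-LUR subjects crossed a threshold since starting lurasidone.

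**Conclusion.** The concern holds as a gap in definition with a conditional consequence. It is certain from the text that 17.4.3 and Table E leave the baseline unnamed where two exist, and that the LT baseline is on-drug for LUR-LUR only. If LT is the reference, LUR-LUR threshold counts leave out change accrued in the first 6 weeks of lurasidone, cannot be set beside PBO-LUR or NR-LUR, and make ALL-EXT a mixture; no other planned output restores the counts.

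The size and direction are not known. The illustrations (9.7% to 11.5% from LT against 12.2% to 19.6% from DB for weight; 1.6% against 1.6% to 3.7% for QTc) show only that the choice can matter under the stated assumptions, and should not be read as estimates for this trial. This is an inexpensive improvement that should be made. It does not undermine the planned safety analysis.

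**What to change.** 1. In SAP 17.4.3 and Table E, state which baseline each change criterion uses.
2. For prior-study completers, tabulate the incidence of QTc increase (30 and 60 msec or more) and of 7% weight change from both DB and LT baseline. For NR-LUR, use LT only. This matches the continuous summaries.
3. For any pooled ALL-EXT incidence, state the reference used. Preferably add a pre-lurasidone version: DB for LUR-LUR, LT for PBO-LUR and NR-LUR. Footnote that elapsed time then differs: at Week 28, about 6 + 28 = 34 weeks for LUR-LUR against 28 for the others.
4. Footnote that post-baseline data start on Day 1 of the long-term study (SAP 6.2), so a rise that came and went within the first 6 weeks is not counted from either baseline.

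There is no need to make the pre-lurasidone baseline the main reference for every row of Table E; naming the baseline is enough for pulse, blood pressure and temperature.

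The cost is a few sentences of SAP text and a few repeat tables. DB values are already required for the planned change summaries. The reported incidences may turn out slightly less favourable.

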17.4.4. SUBGROUP ANALYSIS OF ECG PARAMETERS

The following laboratory parameters will be evaluated for the subgroups specified in section 7.5: QTcB interval and QTcF interval.

Observed, DB baseline and LT baseline and change from DB baseline and LT baseline at Weeks 28 and 28 (LOCF) analyses will be repeated for all subjects up to Week 28 overall and by country (excluding Japan), and

Document: K:\DSP\SM-13496\RVA97109\Biostatistics\Documentation\SAP
Author: [REDACTED] Version Number: 1.0
Version Date: 20MAR2018

Template No: CS_TP_BS016 – Revision 3
Effective Date: 01May2012

Reference: CS_WI_BS005

repeated at Weeks 52 and 52 (LOCF) for all Japanese subjects up to Week 52 overall, by Sex, Age and Mood Stabilizer subgroups separately as well.

Shifts from DB baseline and LT baseline, abnormal ECG values as well as prolonged QTc values will be repeated for all subjects up to Week 28 as well as all Japanese subjects up to Week 52 separately as well.

17.5. VITAL SIGNS

Vital sign results as recorded of the eCRF will be included in the reporting of this study, and will be summarized by treatment group for the safety population.

A Week 28 (LOCF) endpoint and Week 52 (LOCF) endpoint (only for subjects in Japan) will also be derived for Vital Signs. For calculation details, please see section 6.3.

The following Vital Signs measurements will be reported for this study:

- Pulse Rate (bpm)
- Systolic Blood Pressure (mmHg)
- Diastolic Blood Pressure (mmHg)
- Body Temperature (C)
- Weight (kg)
- BMI (kg/m²)

The following summaries will be provided for vital signs data:

- Observed, DB baseline and LT baseline and change from DB baseline and LT baseline by visit
- Incidence of markedly abnormal values (see section 17.5.2)
- Shift from DB baseline and LT baseline to Week 28 (LOCF) and Week 52 (LOCF) endpoints for Body Mass Index (BMI) according to the categories Underweight (BMI < 18.5 kg/m²), Normal (18.5 ≤ BMI < 25 kg/m²), Overweight (25 ≤ BMI < 30 kg/m²) and Obese (BMI ≥ 30 kg/m²).
- Listing of subjects meeting markedly abnormal post-baseline vital signs (MAPVS) criteria (see section 17.5.2)

17.5.1. VITAL SIGNS SPECIFIC DERIVATIONS

$BMI (kg/m^2) = Weight (kg) / Weight (m)^2$.

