- 15) Patients with previous or existing clinically significant complications, such as serious nervous system, endocrine system (including type I diabetes mellitus), hepatic, renal, hematological, respiratory, cardiovascular (including unstable angina, congestive heart failure), gastrointestinal, urological, or other diseases. Patients who have a history of any such diseases and who are considered ineligible for the study by the investigator.
- 16) Patients with acute hepatitis, severe chronic hepatitis or marked hepatic dysfunction.
- 17) Patients with a gastrointestinal disease or a surgical history that may affect drug absorption, distribution, metabolism or excretion.
- 18) Patients with any chronic organic disease of the central nervous system (ie, tumor, inflammation, convulsive seizure, vascular disorder, Parkinson's disease, Alzheimer's disease or other types of dementia, myasthenia gravis, or other degenerative diseases).
- 19) Patients with any mental retardation or persistent neurological findings due to serious head injury.
- 20) Patients with a body mass index (BMI) of $\leq 18 \text{ kg/m}^2$ or $\geq 40 \text{ kg/m}^2$ at screening.
- 21) Patients with previous or existing macular or retinal pigment changes.
- 22) Patients with a previous (within 5 years prior to screening) or existing malignant tumor (excluding appropriately treated basal cell carcinoma of the skin, squamous cell carcinoma, and uterine cervix cancer).
- 23) Patients with a history of neuroleptic malignant syndrome.
- 24) Patients with severe tardive dyskinesia, severe dystonia, or other severe motor dysfunction.
- 25) Patients with an HbA1c (NGSP) value of 8.4% or higher at screening.
- 26) Patients with a history or presence of clinically significant ECG abnormality.
- 27) Patients who have received the study medication (including placebo) in a previous clinical study of SM-13496.
- 28) Patients who are breastfeeding.
- 29) Patients who are currently participating or participated in a clinical study with an investigational or marketed compound or device within 3 months prior to screening or who participated in 3 or more clinical studies within 12 months prior to screening.
- 30) Patients who are otherwise considered ineligible for the study by the investigator.

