6.1 Screening and demographic measurements

The following data will be recorded at screening for patients who did not participate in

the prior study:

- 1) Demographics
 - Date of birth, sex, race, ethnicity, height
- 2) Disease data
 - time of initial onset of bipolar I disorder
 - DSM-IV-TR diagnostic code (regarding severity/psychotic/remission specifiers) of the most recent or current episode
 - time of onset of the most recent or current episode
 - presence or absence of characteristics of rapid cycling disease course
 - number of mood episodes for the consequent 12 months, by episode type
 - time of the most recent hospital discharge if hospitalized because of manic, mixed manic or major depressive episodes
 - number of hospitalizations due to bipolar I disorder
 - psychiatric disease other than bipolar I disorder; diagnosis, DSM-IV-TR diagnostic code, date of onset
- 3) Medical history (only clinical significant history); diagnosis, time of onset, time of remission
- 4) Complications; diagnosis and time of onset
- 5) Mini International Neuropsychiatric Interview (MINI)

The MINI is a short structured diagnostic interview, developed for DSM-IV-TR psychiatric disorders, designed to meet the need for a short but accurate structured psychiatric interview for multicenter clinical trials and epidemiology. Raters at the study site will assess the MINI (version 6.0 10/10/10). The MINI will be utilized to identify other exclusionary psychiatric diagnoses.
- 6) Hepatitis screening; HBs antigen, HCV antibody (Low positive HCV antibody will be confirmed by INNO-LIA method.)

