10. DEMOGRAPHIC AND OTHER BASELINE CHARACTERISTICS

Demographic data and other baseline characteristics summaries will be presented for the safety population by treatment group. Listings will include all enrolled subjects.

No statistical testing will be carried out for demographic or other baseline characteristics.

Summaries will include subjects who completed the prior double-blind study and entered the long-term study, as well as subjects who did not participate in the prior double-blind study and entered the long-term study only. Demographics and baseline characteristics will be carried over from the prior double-blind study for subjects who completed the prior double-blind study.

The following demographic and other baseline characteristics will be summarized and listed. Data points denoted by * are reported in a listing only:

1) Demographics

- Age (years)
- Sex
- Race
- Ethnicity
- Height (cm)
- Country
- Weight (kg)
- Body Mass Index (BMI) (kg/m²)

2) Other Baseline Characteristics

- Baseline Mood Stabilizer

Document:	K:\DSP\SM-13496\RVA97109\Biostatistics\Documentation\SAP	Version Number:	1.0
Author:	[name]	Version Date:	20MAR2018

Template No: CS_TP_BS016 – Revision 3
Effective Date: 01May2012

Reference: CS_WI_BS005

Copyright © 2012 [REDACTED] All rights reserved.
The contents of this document are confidential and proprietary to [REDACTED]
reproduction is strictly prohibited.

Unauthorized use, disclosure or

- o Lithium (mmol/L)
- o VPA (mg/L)
- LT Baseline scores
 - o MADRS total score
 - o CGI-BP-S depression score
 - o CGI-BP-S mania score
 - o CGI-BP-S overall score
 - o YMRS total score

3) Disease data

- Date of initial onset of bipolar I disorder*
- Age at initial onset of bipolar I disorder*
- DSM-IV-TR diagnostic code (regarding severity/psychotic/remission specifiers) of the current major depressive episode or other current episode*
- Date of onset of the current episode*
- Presence or absence of characteristics of rapid cycling disease course
- Number of mood episodes for the consequent 12 months, by episode type
- Date of onset of the most recent major depressive, manic, mixed or hypomanic episode*
- Date of most recent hospital discharge if hospitalized because of major depressive, manic, mixed or hypomanic episodes*
- Number of hospitalizations due to bipolar I disorder (0, 1, 2 or more)
- Psychiatric disease other than bipolar I disorder; diagnosis, DSM-IV-TR diagnostic code, date of onset*

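### The SAP's BMI derivation divides weight by weight squared instead of height squared, so BMI and its shift table would be wrong if programmed as written

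*SAP*

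**What the plan says.** SAP 17.5.1, the section for derivations specific to vital signs, holds a single rule. It sets BMI in kg/m² equal to "Weight (kg) / Weight (m)^2".

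BMI is then used in several places:

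- SAP 17.5 lists BMI among the reported vital signs, with observed values and change from both baselines by visit.
- SAP 17.5 also plans a shift table, from each baseline to the carried-forward endpoints at 28 and 52 weeks, that classifies patients "according to the categories Underweight (BMI < 18.5 kg/m²), Normal (18.5 ≤ BMI < 25 kg/m²), Overweight (25 ≤ BMI < 30 kg/m²) and Obese", the last group starting at 30 kg/m².
- SAP 17.5.3 singles out weight and BMI for extra tables: "For weight and BMI measurements only, summaries for observed, DB baseline and LT baseline and change from DB baseline and LT baseline". These are given by country outside Japan at Week 28, and by sex, age and mood stabilizer for Japanese patients at Week 52.
- SAP 10 lists "Body Mass Index (BMI) (kg/m²") with the demographics.

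On height, Protocol 6.1 has new recruits provide "Date of birth, sex, race, ethnicity, height" at screening, and SAP 10 lists height in cm. For patients from the earlier trial, SAP 10 states: "Demographics and baseline characteristics will be carried over from the prior double-blind study for subjects who completed the prior double-blind study". Height is not among the measurements taken at visits in Protocol 6.3.3, nor among the vital signs listed in SAP 17.5.

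**The concern.** The rule contradicts itself. Weight is not measured in metres, and a result in kg/m² needs a length in the denominator. This is operative text, because the section exists to tell the programmer how to compute the variable.

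Protocol 3.4.2 notes that some atypical antipsychotics affect body weight and metabolism, so a table of movement between BMI categories over 28 or 52 weeks is a safety output that readers will look at. Taken literally, the rule would make that table meaningless. There is also a traceability problem: a program that computes BMI correctly departs from the SAP it is validated against.

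**Working it through.** Neither document states a BMI result, so there is no figure to reproduce. The check evaluates the rule as written and with height in the denominator, then applies the cut-points of SAP 17.5 (18.5, 25 and 30 kg/m²). The weights and heights are illustrative assumptions; the documents give none.

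**Formulas**

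- As written, with recorded weight W in kg: W / W² = 1/W. The printed unit of metres cannot be honoured for a weight, so kilograms are used.
- With height H in metres: W / H².

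**Values**

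| Weight (kg) | Height (m) | As written, 1/W | Category | With height, W/H² | Category |
|---|---|---|---|---|---|
| 45 | 1.60 | 0.0222 | Underweight | 17.6 | Underweight |
| 70 | 1.70 | 0.0143 | Underweight | 24.2 | Normal |
| 80 | 1.70 | 0.0125 | Underweight | 27.7 | Overweight |
| 110 | 1.75 | 0.0091 | Underweight | 35.9 | Obese |

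**Can any patient leave the lowest category?** It would require 1/W ≥ 18.5, that is W ≤ 1/18.5 = 0.054 kg. No patient can. If the rule is applied at baseline and at endpoint alike, every patient is underweight at both and the shift table shows no shifts.

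**Direction of change.** Take a 7% gain from 70 kg, to 74.9 kg, at a height of 1.70 m.

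- As written: 1/74.9 − 1/70 = −0.0009.
- With height: (74.9 − 70) / 1.70² = 4.9 / 2.89 = +1.70 kg/m².

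The literal rule therefore gets the sign wrong as well as the scale.

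**Scale check.** Protocol 4.2.2 excludes new recruits with a BMI of 18 or less, or of 40 or more. An eligible new recruit lies between those limits, and 1/W cannot reach them for any adult weight.

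**Unit of height.** SAP 10 carries height in cm. Replacing the word alone, without converting the unit, would give 70 / 170² = 0.0024 for the 70 kg patient, so the conversion should be stated.

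**The case against.** The strongest reply is that this is a typing slip that corrects itself. The unit (m) beside the second term, the kg/m² on the left and the standard cut-points all point to height. Height is collected, and it sits in the same SAP 10 list as BMI. Because weight in metres does not exist, the rule cannot be run literally at all; the value 0.0143 arises only if someone ignores the unit, puts in kilograms and then accepts BMIs near zero. A programmer or quality check would very likely stop there.

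BMI is also peripheral. Protocol 3.4.2 and SAP 2.2 name body weight, not BMI, as the safety variable. The markedly abnormal weight criterion in SAP 17.5.2 (a change of 7% either way) is computed from weight directly. The study is descriptive and has no hypothesis, so no inference depends on BMI. A fault in reading the PDF cannot be excluded entirely, though it seldom swaps a whole word and leaves the unit intact.

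Most of this stands, and it keeps the point minor. It does not make the rule right: the text is the only BMI derivation in either document, and it is wrong as printed. One could add that the choice of height is largely settled, since no later height is scheduled and completers' demographics are carried over. That is fair, but the derivation neither says so nor mentions the conversion from cm.

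**Conclusion.** The concern holds as stated. The denominator in SAP 17.5.1 is wrong and nothing elsewhere overrides it. If it is programmed as written with weights in kilograms, BMI becomes 1/weight (0.0143 at 70 kg), all patients are classed as underweight, and gains appear as losses. The finding of no shifts assumes that the same rule is used at baseline and after it. If correctly computed BMI values were instead carried over from the prior study as baseline, the 70 kg patient at 1.70 m would show a change of 0.014 − 24.22 = −24.21 kg/m² and would shift from normal to underweight.

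The damage is confined to BMI outputs: the by-visit summaries, the shift table, the subgroup tables and, if the same rule is used there, baseline BMI. Severity is low, because the intent is plain and the literal output would be conspicuously absurd.

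**What to change.** In SAP 17.5.1, define BMI (kg/m²) as weight (kg) at the visit divided by the square of height (m). Add one sentence: height in m is height in cm divided by 100, and the single height recorded at screening (for completers, the height carried over from the prior study) is used at all visits.

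The formula needs one word changed, and the sentence on height makes the source and unit explicit. No new data are needed and no other analysis changes. If the BMI programs already exist, confirm that they use height in metres.
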